9.3.2. Primary Endpoint Analysis

9.3.2.1. Primary Analysis

The primary endpoint is sustained disease control during follow-up. This is a binary variable, assuming the value 1 for a participant free of flare during follow-up and the value 0 for a participant experiencing one or more flares.

The hypothesis test described in Section 9.1 will be carried using logistic regression. Beyond treatment group, the analysis will be adjusted for the stratification factor used in the randomization (country). The outcome of the hypothesis test will be decided upon by the *p* value associated with the treatment group variable. Superiority of TDM over standard of care is claimed if the primary null hypothesis is rejected by a two-sided using significance level of 5% and the treatment difference is in favor of the TDM group.

Missing values of the primary endpoint will be handled using multiple imputation, accounting for both partial missingness on visits as well as visits missed completely.

Adjusted estimates of the probability of sustained disease control within randomization group and their between-group difference will be formed using average risk and risk difference estimators and presented with associated 95% confidence intervals.

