1.3. Schedule of Activities (SoA)

Procedure	Screening	Intervention Period (visit month/visit no)										E/D	Extra Visit	Notes
		Baseline*	2	4*	6	8*	10	12*	14	16	18*			
		Visit 1	Visit 2	Visit 3	Visit 4	Visit 5	Visit 6	Visit 7	Visit 8	Visit 9	Visit 10			
Informed consent	X													
Inclusion and exclusion criteria	X	X												See Sections 5.1 and 5.2
Randomization		X												See Sections 6.3 and 9.3.1
Demography		X												See Section 8.1.1
Height and weight		X												See Section 8.1.1
Medical history including tobacco use		X												See Section 8.1.1
Current medical conditions		X												See Section 8.1.1
Routine laboratory tests		X		X		X		X			X	X	X	Hemoglobin, platelet count, white blood cells with differentials, ALT, creatinine, CRP, ESR. See Section 8.3.1
Biobank full blood		X												All sites See Section 8.1.2
Biobank**		X		X		X		X			X	X	X	Full blood, plasma and serum See Section 8.1.2
Assessment of disease activity		X		X		X		X			X	X	X	DAS28-CRP, EGA, 44 joint count, CDAI, SDAI See Section 8.2.1
Assessment of drug levels and ADAb***		X	X	X	X	X	X	X	X	X	X	X	X	See Section 8.5

RA-FQ, EQ-5D, WPAI:RA		X	X	X	X	X	X	X	X	X	X	X	X	X	See Sections 8.2.1 and 8.8
SF-36, MHAQ, RAID		X		X		X		X		X	X	X	X	X	See Sections 8.2.1 and 8.8
Record of concomitant medication for RA		X		X		X		X		X	X	X	X	X	See Section 6.9.2
AE registration		X		X		X		X		X	X	X	X	X	See Section 10.3
Adherence		X	X	X	X	X	X	X	X	X	X	X	X	X	By questionnaires and digital calendar See Section 6.5
	
*Onsite hospital visits ** Participants at Diakonhjemmet Hospital only ***In all participants AE = Adverse Events; ALT=Alanine Transaminase; E/D = Early Discontinuation; EGA = Evaluators Global assessment of disease activity; ESR= Erythrocyte sedimentation rate; EQ-5D = European Quality of Life 5 Dimensions; Ex visits = Extra visit if flare; CDAI = Clinical disease activity index; CRP= C-reactive protein; DAS28-CRP = Disease Activity Score using 28 joints C-reactive protein; MHAQ = Modified Health Assessment Questionnaire; PGA = Patient Global assessment of disease activity; RAID = Rheumatoid Arthritis Impact of Disease; RA-FQ = Rheumatoid Arthritis Flare Questionnaire; SDAI = Simple disease activity index; SF-36= 36-Item Short-form health survey; WPAI:RA = Work Productivity and Activity Impairment Questionnaire: Rheumatoid Arthritis
														

2. Introduction

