
 • To assess cost effectiveness, utility, and impact on quality of life of proactive TDM compared to standard of care • To assess whether biomarkers (including genetic markers) and other factors can predict development of ADAb in participants on SC TNFi • To study how serum drug levels and ADAb are associated with drug efficacy and safety • To study predictors of flare and treatment response • To study differences in immunogenicity between different SC TNFi • To characterize anti-drug immune responses, including ADAbs isotypes, epitopes, and association to genetic markers (e.g., HLA) • To assess how TDM influences treatment with respect to serum drug/ADAbs levels and disease activity • To assess efficacy of TDM in the subgroup of participants with ADAbs • To study feasibility of TDM and compliance to the treatment algorithm • To study the performance of the treatment strategy within the group of participants affected by the algorithm • To study the effect of dose escalation/decrease on serum drug levels and clinical outcomes • To study the value of TDM in the setting of switching of drug to a different bDMARD • To study effectiveness of TDM in subgroups of participants where TDM is assumed to be particularly valuable, including participants with high disease activity at baseline, participants not on immunosuppressive co-medication, and participants with previous secondary loss of effect of TNFi • To study adherence • To study corticosteroid consumption • To study different measures for assessing flares 	
 • European Quality of Life 5 Dimensions (EQ-5D, 36-Item Short-form health survey (SF-36), Work Productivity and Activity Impairment Questionnaire: Rheumatoid Arthritis (WPAI-GH) • Genetic markers and biomarkers • Assessments of serum drug levels and ADAbs • Assessments of AE • DAS28-CRP, Joint count of 44 joints, PGA, EGA, CDAI, SDAI, RAID, MHAQ, ACR/EULAR remission criteria • Biochemical parameters (including CRP and ESR) • Drug survival • Adherence questionnaire • Drug calendar • Co-medication assessment • Rheumatoid arthritis flare questionnaire (RA-FQ)

4. Study Design

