8.2.2. Definition of Flare

A flare is defined as a combination of an increase in DAS28-CRP of 1.2 units, or 0.6 if DAS28-CRP \geq 3.2, AND at least 2 swollen joints on examination of 44 joints (39, 40, 53).

If a participant does not fulfil the formal definition, but experiences a clinically significant worsening, according to both the investigator and participant, that leads to a major change* in treatment, this should be considered as a flare but be recorded separately in the eCRF.

*A major change in treatment includes:

- Switching to another bDMARD or a tsDMARD
- Adding a csDMARD
- Increasing the dose of a concomitant csDMARD
- Adding or increasing systemic glucocorticoids (per orally, intravenous or intramuscular)
- Receiving more than one intra-articular glucocorticoid injection at one visit
- Shortening the interval of the SC TNFi for clinical reasons (Standard of care group)

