The Work Productivity and Activity Impairment (WPAI) questionnaire is a tool that assesses impairments in both work and daily activities. It consists of six items that determine employment status and measure absenteeism caused by health issues, presenteeism, and overall health-related impairment in both paid work and regular activities over the preceding 7 days. The questionnaire yields four outcomes: i) the percentage of work time missed due to health; ii) the percentage of impairment experienced while working due to health in the past 7 days; iii) the percentage of overall work impairment; iv) activity impairment resulting from health issues. Participants will be asked to answer the Work Productivity and Activity Impairment Questionnaire: Rheumatoid Arthritis V2.0 (WPAI:RA) (61, 62). See Appendix 16.

9. Statistical Considerations

The statistical analyses are planned to be carried out when:

- The planned number of participants have been included
- Each included participant has completed their end-of-study visit, withdrawn, or been withdrawn according to protocol procedures
- All data from the study period have been entered, verified, and validated according to the data management plan

Prior to the statistical analysis, the data will be locked from further entering or editing. A SAP will be finalized prior to any analysis of treatment effects. The SAP will include a more technical and detailed description of the statistical analyses described in this section. This section gives a summary of the planned statistical analyses of the most important endpoints, including the primary endpoint and some key secondary endpoints. The SAP will be finalized, signed, and dated prior to database lock. Any deviation from the original statistical plan will be described and justified in the CSR.

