9.1.1. Multiplicity Adjustment

Only a single hypothesis test will be carried out, and only the p value associated with this comparison will be reported. No other hypothesis test will be carried out or p values reported, hence adjustment for multiplicity is not needed. All other comparisons will be descriptive and, where appropriate, accompanied by confidence intervals (unadjusted for multiplicity).

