9.3.2.2. Sensitivity Analysis

Sensitivity analyses will include additional approaches to dealing with missing values of the primary endpoint, possibly including, but not limited to, complete-case analysis, last-observation carried forward imputation, and worst-case imputation (i.e., imputing missing values as flare). Additional analyses may include adjustment for unbalanced baseline covariates such as age, sex, and co-medication.

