9.3.2.3. Supplementary Analysis

The primary outcome will also be analyzed using Cox proportional-hazards regression. The time of first flare will serve as the event time, which for participants that are free of flare during follow-up will be censored at the last visit date. For this analysis, an assumption of independent censoring will be used, and adjustment for stratification factors used in the randomization will be made.

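### Free improvement, not an error: the primary logistic and Cox models adjust for country only and leave out baseline DAS28-CRP, which is collected in everyone and plausibly prognostic

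*Protocol*

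**What the plan says.** **Primary model.** Section 9.3.2.1 fixes the covariates of the logistic model: "Beyond treatment group, the analysis will be adjusted for the stratification factor used in the randomization (country"). The p value for treatment group decides the test. Group-specific average risks and their difference are reported with 95% confidence intervals.

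**Cox model.** Section 9.3.2.3: "For this analysis, an assumption of independent censoring will be used, and adjustment for stratification factors used in the randomization will be made". Country is the only stratification factor (Sections 6.3 and 9.3.1).

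**Further adjustment.** Section 9.3.2.2: "Additional analyses may include adjustment for unbalanced baseline covariates such as age, sex, and co-medication".

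**Baseline DAS28-CRP.** The Schedule of Activities (Section 1.3) lists "DAS28-CRP, EGA, 44 joint count, CDAI, SDAI" at baseline for all participants, and inclusion criterion 4 (Section 5.1) requires a value below 3.2. Section 8.2.2 defines the formal flare route: "A flare is defined as a combination of an increase in DAS28-CRP of 1.2 units, or 0.6 if DAS28-CRP" is at least 3.2, together with at least two swollen joints among 44. A second route is agreement between participant and physician on a worsening that leads to a major treatment change.

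**Status of the plan.** Section 9 (opening text): "A SAP will be finalized prior to any analysis of treatment effects". Section 9.1.1: "Only a single hypothesis test will be carried out, and only the p value associated with this comparison will be reported".

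**The concern.** Part of the endpoint is a change in a score whose starting value is known for everyone, yet that starting value is in neither model. If it predicts flare, a model that includes it uses the same data more efficiently and deals with a chance imbalance in that value without a decision made after seeing the data. At stake is a small amount of power and some robustness to chance imbalance. The validity of the test is not in question.

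A lesser matter is the criterion in Section 9.3.2.2. In a randomized trial baseline imbalance arises by chance, so choosing covariates because they turned out unbalanced makes the choice depend on the observed data. Expected prognostic value, judged beforehand, is the better criterion.

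**Working it through.** **1. The plan's own figure.** Inputs from Section 9.5: 72.5% against 85%, two-sided 5%, 1:1 allocation. With unpooled variance:

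- Variance sum: 0.725 × 0.275 + 0.85 × 0.15 = 0.1994 + 0.1275 = 0.3269.
- 80% power: n per arm = 0.3269 × (1.960 + 0.842)² / 0.125² ≈ 164.2, so 165 per arm and 330 in total.
- 90% power: the same formula with 1.282 gives 220 per arm and 440 in total.

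Both match Table 2. No covariate enters the calculation, so this point overturns no stated figure.

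**2. Why baseline may be prognostic.** Suppose the increase is counted from baseline value b and the 3.2 condition refers to the value at the flare visit. The protocol states neither. The rise needed is then about:

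- 1.2 if b is 2.0 or lower;
- 3.2 − b if b lies between 2.0 and 2.6;
- 0.6 if b is above 2.6.

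Someone who enters close to 3.2 needs half the rise of someone who enters at 2.0 or below. This makes a link plausible but does not prove it: the swollen-joint condition and the consensus route also determine flare. Section 3 lists "To study predictors of flare and treatment response" only as an exploratory objective.

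**3. Power with and without baseline.** The protocol gives no prognostic strength, so an odds ratio (OR) per standard deviation (SD) is assumed. Marginal rates are held at 72.5% and 85%, with three countries and a linear baseline term. Main simulation: 36,000 trials per setting, N = 350.

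| Assumed OR per SD | Country only | Country + baseline | Gain (points) |
|---|---|---|---|
| 1.0 | 81.9% | 81.9% | 0.0 |
| 1.25 | 82.0% | 82.3% | +0.3 |
| 1.5 | 81.9% | 82.8% | +1.0 |
| 2.0 | 81.4% | 84.3% | +2.9 |

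The Monte Carlo standard error of the gains is 0.05 to 0.13 points. Two separate simulations agree:

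- 4,000 trials per setting: 0.0, +0.5 and +2.5 points at ORs of 1.0, 1.5 and 2.0.
- A third run: about +0.1, +0.4, +0.4 and +2.4 points at 1.0, 1.25, 1.5 and 2.0.

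With 306 analysed (350 × 0.875) the gains are 0.0, +0.3, +1.1 and +2.9 points.

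**4. Applying the flare thresholds.** In 16 scenarios that apply the protocol's DAS28-CRP thresholds (4,000 trials each, N = 350), the linear term gained −0.2 to +3.2 points, and less than 1 point in 14. The two larger gains came from scenarios with no consensus-route flares.

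**5. Cost of the extra term.** Under the null (72.5% in both arms), rejection in favour of TDM was 2.4–2.5% with country only and 2.3–2.6% with baseline added, against a nominal 2.5%. Expected flares are 175 × 0.275 + 175 × 0.15 = 74.4 with 350 analysed, or 153 × 0.275 + 153 × 0.15 = 65.0 with 306. One more model term is affordable.

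**6. Chance imbalance.** The standard error of the arm difference in baseline is √(4/350) = 0.107 SD, so two standard errors are 0.214 SD. The simulated shift in the risk difference per SD is 0, 3.60, 6.48 and 10.48 points at the four ORs. Multiplied by 0.214 this gives 0, 0.8, 1.4 and 2.2 points, against a planned difference of 12.5.

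**The case against.** The strongest reply is that nothing here is wrong. Adjusting for the stratification factor is valid, it is done consistently in both models, and adding a covariate is a matter of preference. The gain is assumed rather than derived, and every threshold scenario that included the consensus route gained less than 1 point. Section 9.3.2.2 describes optional analyses that the SAP may still pin down. The runs with 306 analysed also shrink the sample, whereas the protocol plans multiple imputation.

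Most of this stands, and it limits the point to an optional improvement. It does not remove it. Section 9.3.2.1 itself fixes the covariate set, so the suggestion changes stated text rather than filling a gap left to the SAP, and the simulations show no meaningful loss when baseline is not prognostic.

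Three stronger readings are tempting, and the protocol supports none of them:

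- **The country-only test is biased or inflates type I error.** It is not and does not; see the null results in step 5.
- **About 3 points of power are being lost.** That needs a strong prognostic link, for which the protocol gives no evidence.
- **The imbalance criterion lets the data steer the main result.** Only one test is planned, so it cannot. If unbalanced meant p < 0.05, chance would flag at least one of three independent covariates in 1 − 0.95³ = 14.3% of trials. The protocol states no such rule, and the rate would bear only on optional analyses with no planned test.

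**Conclusion.** The point holds as a low-priority suggestion. The country-only models are valid and fully specified. Adding baseline DAS28-CRP would use a value already collected in everyone. The expected gain is about 0 to 1 percentage point of power for odds ratios per SD up to 1.5, and about 2.5 to 3 points at 2.0. The lower range is the more likely one, given the threshold scenarios. These figures rest on an assumed prognostic strength, a linear effect, and the protocol's 72.5% and 85%. The wording in Section 9.3.2.2 is a secondary matter with no effect on the confirmatory conclusion.

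**What to change.** By early protocol amendment to Sections 9.3.2.1 and 9.3.2.3, carried into the SAP and made before any treatment comparison:

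- Add baseline DAS28-CRP to both models as one continuous covariate beside country, with its form (linear, or one named alternative) fixed in advance.
- Keep the planned average-risk and risk-difference estimators, so that the reported effect stays on the same scale.
- Keep the country-only logistic model as a sensitivity analysis.
- In Section 9.3.2.2, replace the reference to unbalanced covariates with a list chosen beforehand for expected prognostic value and used whatever imbalance is seen. Age, sex and co-medication may be on it.

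Changing the SAP alone is not enough for the primary model, because the SAP would then disagree with the covariates fixed in Section 9.3.2.1.

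The cost is one amendment with ethics committee approval (Section 10.1.1) and one model term. No new data are needed. Timing matters: the trial is open-label (Section 6.4), so a late change to the confirmatory model would weaken the pre-specification it is meant to strengthen.

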9.3.2.2. Sensitivity Analysis

Sensitivity analyses will include additional approaches to dealing with missing values of the primary endpoint, possibly including, but not limited to, complete-case analysis, last-observation carried forward imputation, and worst-case imputation (i.e., imputing missing values as flare). Additional analyses may include adjustment for unbalanced baseline covariates such as age, sex, and co-medication.

9.3.2.3. Supplementary Analysis

The primary outcome will also be analyzed using Cox proportional-hazards regression. The time of first flare will serve as the event time, which for participants that are free of flare during follow-up will be censored at the last visit date. For this analysis, an assumption of independent censoring will be used, and adjustment for stratification factors used in the randomization will be made.

9.3.2.4. Subgroup Analyses

Subgroup analyses of the primary endpoint according to each TNFi type (if more than one TNFi type is included) will be carried out.

9.3.3. Secondary Endpoint Analyses

The between-group comparisons for secondary variables will be carried out in a manner similar to the primary endpoint where applicable and analyses will be performed based on the following methods (but not limited to):

- Continuous secondary variables will be analyzed by linear regression, using mixed effects for repeated measures, or appropriate non-parametric alternatives
- Binary response variables will be analyzed using logistic regression (possibly adjusting for within-subject dependencies by mixed model approaches)
- Time-to-event variables will be analyzed using the Kaplan-Meier method, Cox regression analysis, and/or appropriate parametric models such as the Weibull model.

9.4. Interim Analysis

No interim analysis is planned.

9.5. Sample Size Determination

A minimum of 350 participants will be randomized.

The sample size calculation is based on the primary outcome, sustained disease control throughout 18 months of follow-up, and an assumption that TDM will increase the probability of sustained control by 12.5 percentage points: from an assumed 72.5% for patients treated according to Standard of care to 85% for those whose treatment includes TDM. Requiring 80% power to reject the primary null hypothesis, this implies that at least 350 participants are needed, assuming a 10-15% drop-out rate. However, if the inclusion rate is sufficiently high, the trial steering committee could decide to increase the sample size to a maximum of 450 patients to achieve a higher power of 90% (Table 2). Sample sizes corresponding different combinations of power and effects of TDM (assuming the same 72.5% sustained remission rate in the Standard of care group, but without allowance for drop-out) are given in Table 2.

Table 2. Power Calculations

Power	Difference in sustained disease control 10%	Difference in sustained disease control 12.5%	Difference in sustained disease control 15%
-------	---	---	---

80%	540	330	216
90%	724	440	290

The assumed rates are based on data from two prior studies, the NOR-DRUM B and ARCTIC Rewind trials (33, 38, 63). Regarding the effect of TDM versus standard of care, the first of these estimated that the hazard rate of disease flare in patients on maintenance infliximab treatment without TDM was about twice that of those whose treatment included TDM. Regarding the flare rate associated with standard care, in the NOR-DRUM B trial 22 of 40 (55%) RA patients in the standard of care group did not experience a disease flare during 12 months of follow-up, whereas in the ARCTIC Rewind trial, which also had a 12-month follow-up period, the numbers were 41 of 45 patients (91%). The disease flare definition used in the current study is similar to the one employed in the ARCTIC Rewind trial, while the one in NOR-DRUM B was more liberal. However, the present inclusion requirement of a remission duration of at least 3 months is less stringent than in the ARCTIC Rewind trial (12 months), but more so than in the NOR-DRUM B trial (none). Based on this, it seems reasonable to expect that approximately 80% of those in the standard of care group will be free of disease flare during the first 12 months of follow-up.

Assuming constant hazards (i.e., exponential survival times), this implies a daily hazard rate of flare around 0.0006 in the Standard of care group (since $\exp(-0.0006*365) = 0.80$) and, assuming a similar hazard ratio as in the NOR-DRUM B trial, 3.0e-4 in the TDM group. With these assumptions, it follows that 72.5% in the Standard of care group are expected to be flare-free during the 18 months of follow-up compared to an expected 85% in the TDM group(*)).

(*) Since, $= \exp(-0.0006*365*1.5) = 72.5\%$ and $\exp(-0.0003*365*1.5) = 85\%$.

10. Supporting Documentation and Operational Considerations

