5.1. Inclusion Criteria

Participants are eligible to be included in the study only if *all* of the following criteria apply:

1. A clinical diagnosis of RA
2. ≥ 18 and < 75 years of age at screening
3. On stable therapy with standard dose of a SC TNFi (adalimumab) for a minimum of 3 months and a maximum of 24 months
4. In low disease activity or remission (DAS28-CRP < 3.2) and indication for continuation of treatment according to the treating physician
5. Subject capable of understanding and signing an informed consent form

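### By Section 9.5's own Table 2, 350 participants give 80% power with about 6% drop-out, not the stated 10–15%, and the control rate is derived with an arithmetic slip and a criterion that Section 5.1 lacks

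*Protocol*

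**What the plan says.** Section 9.5 of the protocol assumes 72.5% sustained disease control under standard of care and 85% under TDM, and concludes: "Requiring 80% power to reject the primary null hypothesis, this implies that at least 350 participants are needed, assuming a 10-15% drop-out rate". Table 2 gives 330 (80% power) and 440 (90% power) for that difference, and the text says its entries assume the same control rate, "but without allowance for drop-out) are given in Table 2". If recruitment goes well, the steering committee may "increase the sample size to a maximum of 450 patients to achieve a higher power of 90% (Table 2".

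The rates are derived from daily hazards of 0.0006 and 0.0003 over 18 months: "With these assumptions, it follows that 72.5% in the Standard of care group are expected to be flare-free during the 18 months of follow-up". The hazard of 0.0006 itself comes from a judgement that about 80% of control participants stay flare-free for 12 months. That figure lies between 55% and 91% in two earlier trials, and one reason given for placing it there is that "the present inclusion requirement of a remission duration of at least 3 months is less stringent than in the ARCTIC Rewind trial" but more stringent than in the other trial.

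Two other sections bear on this. Section 9.3.2.1 says: "Missing values of the primary endpoint will be handled using multiple imputation". Section 5.1 lists the entry criteria as "On stable therapy with standard dose of a SC TNFi (adalimumab) for a minimum of 3 months and a maximum of 24 months" and "In low disease activity or remission (DAS28-CRP < 3.2) and indication for continuation of treatment according to the treating physician".

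**The concern.** The paragraph gives 330 without drop-out and 350 with 10–15% drop-out for the same scenario. Twenty extra participants are about 6% of 350, so the two figures and the drop-out rate cannot all be right. The 90% figure for 450 rests on Table 2 and so contains no drop-out, yet it stands directly after an 80% figure said to include it. Anyone comparing the two sizes, including the steering committee, would be comparing unlike quantities.

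The control rate has two weaknesses of its own. The printed exponential does not evaluate to 72.5%. The remission-duration argument behind the 12-month rate also refers to an entry requirement that Section 5.1 does not set.

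At stake is whether the stated power follows from the plan's own assumptions. The validity of the primary test is not in question.

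**Working it through.** **Inputs.** Two-sided 5% test (Section 9.1); 1:1 allocation (Section 9.3.1); 72.5% against 85%, power 80% or 90%, drop-out 10–15%, N = 350 or 450 (Section 9.5).

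**1. Reproduce Table 2.** Unpooled two-proportion formula, per arm:

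n = (z₀.₉₇₅ + z_power)² × [p₁(1−p₁) + p₂(1−p₂)] / (p₂−p₁)²

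The variance sum is 0.725×0.275 + 0.85×0.15 = 0.3269, and the squared difference is 0.015625.

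- 80% power: 7.849 × 0.3269 / 0.015625 = 164.2 per arm. The total is 328.4, or 330 when rounded up per arm.
- 90% power: 10.507 × 0.3269 / 0.015625 = 219.8 per arm. The total is 439.6, or 440 when rounded up per arm.

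The same formula returns all six cells (540/330/216 and 724/440/290), so the method behind Table 2 is not in doubt.

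**2. Add drop-out, N/(1−d).**

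| | 10% | 15% |
|---|---|---|
| 80% power | 330/0.90 = 367 | 330/0.85 = 389 |
| 90% power | 440/0.90 = 489 | 440/0.85 = 518 |

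The largest drop-out that keeps the stated power is 1 − 328.4/350 = 6.2% at 350 and 1 − 439.6/450 = 2.3% at 450.

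**3. Power if drop-outs contribute nothing (72.5% vs 85%).**

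| Randomised | no drop-out | 10% | 12.5% | 15% |
|---|---|---|---|---|
| 350 | 82.4% | 78.3% | 77.2% | 76.0% |
| 450 | 90.7% | 87.5% | 86.6% | 85.6% |

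A pooled-variance formula gives values 0.5–0.7 points lower.

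**4. Power if imputation recovers all follow-up before drop-out.** The protocol gives no timing of drop-out, so I assume a constant drop-out hazard c alongside a constant flare hazard h. With time scaled to the 18 months, the Greenwood variance per participant is S² h (e^(h+c) − 1)/(h + c). Compared with S(1−S), and summed over arms, efficiency is 0.946 / 0.932 / 0.918 at 10 / 12.5 / 15% drop-out. Power is then:

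- 350: 80.3% / 79.7% / 79.1%
- 450: 89.1% / 88.6% / 88.1%

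**5. The rates.** exp(−0.0006×365×1.5) = exp(−0.3285) = 72.0%, and exp(−0.0003×365×1.5) = exp(−0.16425) = 84.9%. The TDM figure rounds to the printed 85%; the control figure does not round to 72.5%. The difference becomes 12.85 points.

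- These rates need 314 evaluable, hence 349 at 10% drop-out and 370 at 15%.
- With no information from drop-outs, 350 gives 80.2% / 79.1% / 77.9% and 450 gives 88.9% / 88.1% / 87.2%. The stated power holds up to 10.4% drop-out at 350 and 6.7% at 450.
- Combined with the imputation reading of step 4, 350 gives 82.1–80.9% and 450 gives 90.4–89.5%.

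**6. The entry criterion.** Section 9.5 refers to at least three months of remission. In Section 5.1 the three months attach to stable therapy at standard dose. Disease activity is a threshold at inclusion (DAS28-CRP below 3.2) that admits low disease activity as well as remission, and no duration of control is set. Section 4.1 describes the population in the same way.

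**The case against.** The strongest reply is that 367–389 treats every drop-out as carrying no information, which the plan does not do. It imputes missing outcomes, keeps participants who stop treatment in follow-up (Sections 6.1.3 and 7.1), and already knows the outcome of anyone who flares before leaving. On the imputation calculation above, the shortfall at 350 is at most 0.9 points, and later drop-out or richer imputation could recover more. This stands as a limit on the size of the problem. It does not make the sentence correct, because Section 9.5 claims a drop-out allowance and does not invoke imputation.

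A second reply is that the upstream assumptions nearly support 350. An exact 80% at 12 months with a hazard ratio of 2 gives 0.80^1.5 = 71.6% and 0.80^0.75 = 84.6%. These need 308.5 evaluable, or 343 at 10% and 363 at 15%. Then 350 keeps 80% power up to 11.9% drop-out, with 80.8% / 79.7% / 78.6% at 10 / 12.5 / 15%. This probably explains much of the gap, but it still misses the upper end of the range, and neither the stated 72.5% and 85% nor Table 2 uses these rates.

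Third, 72.0% against 72.5% may be only rounding: a hazard of 0.000587 gives 72.5% at 18 months and 80.7% at 12 months. That is fair, and the slip makes the requirement larger rather than smaller. The printed equality is still wrong.

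Fourth, the 450 sentence cites Table 2, which is declared free of drop-out, and the trigger for expansion is the inclusion rate. The 90% is indeed correct on that basis (90.7%). What remains is that it sits unexplained beside a figure on a different basis.

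Finally, 350 is a floor and up to 450 is allowed. However, the text ties that floor to 80% power at 10–15% drop-out.

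**Conclusion.** The concern holds. On the section's stated rates and its own Table 2, 350 randomised participants deliver 80% power only up to about 6% drop-out, and 450 deliver 90% only up to about 2%. At 10–15% drop-out the shortfall is about 0–4 points at 350 and 1–4 points at 450. The upper ends assume drop-outs contribute nothing. The lower ends assume imputation recovers all earlier follow-up under a constant drop-out hazard, which the protocol neither states nor excludes. Roughly the stated powers are reached at both sizes only when the hazard-derived rates and the imputation gain are taken together.

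The 72.5% is a small numerical error. The remission-duration argument rests on a criterion the protocol does not have; its effect on the 80% control rate cannot be quantified from the document. None of this affects the test, the significance level or the conduct of the trial. It should be corrected because the power as written does not follow from the section's own figures.

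**What to change.** Revise Section 9.5 as follows.

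1. State that, at 72.5% against 85%, 80% power at 350 and 90% at 450 hold only up to about 6% and 2% drop-out. Add that at 10–15% drop-out power is about 76–78% and 86–88% before any gain from multiple imputation. If a gain is claimed, give the drop-out pattern assumed.
2. Use one set of rates throughout. Either correct the exponential to 72.0% and recompute Table 2, or print the hazard to enough digits to give 72.5%.
3. Replace the remission-duration sentence with the criteria in Section 5.1 and justify the 80% control rate at 12 months on that basis.

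The cost is wording only. No additional participants are required; the stated power becomes slightly less favourable.
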